15.0 Risks to Subjects*

15.1 List the reasonably foreseeable risks, discomforts, hazards, or inconveniences to the subjects related to the subjects' participation in the research. Include as may be useful for the IRB's consideration, a description of the probability, magnitude, duration, and reversibility of the risks. Consider physical, psychological, social, legal, and economic risks.

The intervention that was tested in the original Omega Tots trial may have lasting effects on child development and behavior. It is currently not foreseeable if that prior intervention may have effects at ages 8½ - 10 ½ years that are negative, that is a question to be answered by the research.

All of the research related procedures, surveys, and questionnaires, are designed to meet the definition of “minimal risk” in the federal regulations [§45 CFR 46.102(i)] and to be reviewed by IRBs under §45 CFR 46.404 “Research not involving greater than minimal risk.” Minimal risk as defined in the federal regulations means “that the probability and magnitude of harm or discomfort anticipated in the research are not greater, in and of themselves, than those ordinarily encountered in daily life or during the performance of routine physical or psychological examinations or tests.” In addition, the Study Staff is committed to minimizing risks even when the risks are minimal.

The informed consent process takes place in private. It is possible some participants may feel uncomfortable or upset when answering survey questions. However, questionnaires are structured to avoid creating discomfort for the research participants; and participants are reminded at each data collection encounter that participation is voluntary, they have the right to withdraw from the research project at any time, and they may refuse to answer or may skip any question.

The risks of collecting and storing linked clinical data and biospecimens are primarily psycho-social. Developing coding strategies to mitigate these risks is a fundamental ethical requirement of the study. Potential harm could result from a breach of confidentiality. One of the primary concerns is that employment and insurance discrimination might result from exposure of information about health history, genetic makeup, or familial predisposition to disease. The risk is minor, especially since unique participant identifiers will not be stored with biospecimens. Moreover, the study will maintain confidentiality of the data in its databases. Finally, the genetic data to be studied in this phase of research have not been shown to be highly predictive of risk for any particular disease. Data submitted to the study does include participant identifiers, as defined by the U.S. Health Insurance Portability and Accountability Act of 1996 (HIPAA). All participant data will be maintained in secure databases and files by number code. The study will follow all necessary measures to assure the data are protected and secure from unauthorized access. Only IRB-approved study personnel will have access to the file that links names to identification numbers. Data will be summarized in aggregate for reporting purposes. All electronic information is stored on the

PROTOCOL TITLE: Long-term Effects and Safety of DHA+AA Supplementation in Toddlerhood for Children born Preterm

secure network and available only to study personnel. All paper files will be secured in a locked room in the Center for Biobehavioral Health. Based on the research team's experience with previous studies, these methods of data confidentiality and protection have been effective.

Experienced research staff will perform biospecimen (i.e. saliva) collections with participants, via saliva tube. This method was selected in lieu of phlebotomy, in order to decrease pain and discomfort of research participants; phlebotomy is a participation barrier and we are keen to maximize enrollment, minimize discomfort and reduce study risks. Saliva collection procedures involve minimal discomfort. Saliva collection will be described using colorful drawings, and collectors will pantomime the procedure to ensure complete comprehension prior to beginning administration, to reduce as much mental or physical discomfort as possible. An alternative, sponge collection method will be offered if the child has difficulties with the saliva collection. The parent may also be present to support the child during saliva collection, if the child finds it unpleasant. All staff involved in collection of biospecimens will be credentialed accordingly by trained investigator staff.

The genetic tests are highly unlikely to identify new information on disease mutations. This research will not include mapping participant's DNA (whole genome sequencing). Families will be encouraged to ask the study team if they have questions.

Although we do not conduct medical tests (the kind that can be ordered by a doctor), and we do not believe any of our tests have medical value, it is possible that, in the future, other researchers may decide that our tests may be medically important.

Child abuse protections will be in effect as study staff are mandated reporters trained to identify signs of abuse or neglect. Standard operating procedures have been developed and implemented under the Principal Investigator's leadership of past studies to protect the well-being of children. The same protocol will be implemented for this study. Study staff will be trained in mandated reporting procedures based on curriculum developed especially for studies in the Center for Biobehavioral Health by the NCH Department of Social Work and the PI in conjunction with guidelines and procedures of the Franklin County Department of Children's Services. Safety oversight will be under the direction of the PI. If medical intervention is required in the case of an adverse event, children may seek care at Nationwide Children's Hospital or their personal physician.

The knowledge to be gained from this investigation outweighs these minimal risks. We do not anticipate any risks to others who are not study participants, nor any additional or unforeseeable risks. This study has the potential to inform future dietary recommendations for children, especially those who were born preterm.

16.0 Potential Benefits to Subjects

The intervention that was tested in the original Omega Tots trial may have lasting effects on child development and behavior. It is currently not foreseeable if that prior intervention may have effects at ages 8 ½ - 10 ½ years that are positive, that is a question to be answered by the research.

There are no known potential benefits from follow-up participation. Participation in this study will aid in acquiring new knowledge that might help other children who are born prematurely and their families in the future. There are no other known benefits expected from participation in this study. However, the child

PROTOCOL TITLE: Long-term Effects and Safety of DHA+AA Supplementation in Toddlerhood for Children born Preterm

may enjoy the small book or gift to thank them for their time, or find some of the data collection procedures entertaining (e.g. iPad assessments).

17.0 Data Management and Confidentiality

17.1 Data analysis plan

Statistical power and sample size for Aim 1:

All 377 children randomized in Omega Tots will be eligible for follow-up. We estimate power based on a conservative estimate of 300 children (80%) attending the age 8 ½ - 10 ½ visit. To evaluate differences between the treatment arms, 300 children divided equally to each arm provides >80% power to detect a 0.32-SD mean difference or larger (Cohen's $d \geq 0.32$) in each of our primary outcome measures: DAS-II GCA (general cognitive ability), CELF-Core Language (language), or Toolbox Executive Function factor (EF) ($\alpha=0.05$) at age 8 ½ - 10 ½ (Hypothesis 1). This effect size is the same or smaller than what the DINO trial observed on the BRIEF at age 7, and the short (ECBQ) and follow-up (DP-3 at age 2) results from Omega Tots. These effect sizes are also similar in magnitude to the (beneficial) effect observed in the Infant Health and Development Program early intervention trial at age 8 on IQ and reading and math achievement among infants born at 2000-2500g. Sub-group analyses will necessarily be exploratory because only a much larger sample would be fully powered to test the interactions of interest. But, these are worth exploring because in the original Omega Tots trial we observed 2 statistically significant sub-group effects. Although it would be ideal to employ a repeated measures analysis using the 3 available time points (trial, age 2, age 8 ½ - 10 ½), robust developmental measures that are comparable at all time points are not available. We will pursue longitudinal analyses for the secondary outcomes where repeated measures exist, however.

Statistical analysis for Aim 1:

Analyses for Aim 1 will follow intent to treat principles, the most rigorous approach to RCT data. By using intent to treat we are able to detect lasting effects of DHA+AA supplementation if they are present at the magnitude we anticipate. Children who were randomized but discontinued taking treatment or were lost to follow-up will be included in analyses. Our main goal will be to estimate the effect of treatment assignment on our 3 primary outcomes at age 8½ - 10 ½ (DAS-II GCA, CELF-5 language, Toolbox EF) using the following mixed model, consistent with the analysis of our Omega Tots trial: $y_{it} = \beta_0 + \beta_1 Time_t + \beta_2 Time_t \times Trt_i + \epsilon_{it}$, where implicitly it is assumed that there is no main effect of Trt_i , y_{it} is the outcome of interest at time t , $Time_t$ is coded as 0 for the outcome at baseline (i.e., the covariate for our purposes here) and 1 for the post-randomization measure of the outcome obtained at age 8 ½ - 10 ½, and the primary effect of interest is β_2 , which corresponds to the difference between groups on the outcome at age 8 ½ - 10 ½. In this model, the baseline measure of the outcome is constrained to have equal means across groups by assuming there is no main effect of the intervention, Trt_i . This constraint yields a statistical test for β_2 analogous to the test of the treatment group main effect via ANCOVA controlling for the baseline measure without requiring list-wise deletion due to missing data. Specifically, our model is estimated using maximum likelihood estimation, and therefore allows for outcome data at either time point to be missing at random. We will account for clustering due to twins/triplets in our sample by adding a random effect at the family level. Exploratory pre-specified sub-group analyses will proceed by testing interaction terms added to the models for sex, birthweight (<1500g vs ≥ 1500 g), socioeconomic (household income dichotomized at the median), and daily dietary intake of DHA plus EPA (below vs above the median).

PROTOCOL TITLE: Long-term Effects and Safety of DHA+AA Supplementation in Toddlerhood for Children born Preterm

Interactions with $p < .20$ will be considered statistically significant, and stratified results will be reported consequently. Analyses will use the MIXED procedure, SAS 9.4.

Statistical power, sample size, and analysis for Aim 2 (i.e. genetic biospecimens):

To address the first part of Aim 2, we apply the standard method for estimating SNP-based heritability, which assumes the common SNP effect is a random effect in a mixed linear model and with variance decomposed into variance components for genetic and non-genetic effects. The generic model is therefore specified as: $y = \beta_0 + X\beta + g + \epsilon$, where g is the random genetic effect and further the model is constrained by $V = A\sigma_g^2 + I\sigma_e^2$ where V is the overall variance decomposed into genetic and non-genetic (i.e. environmental) components; the matrix A is the genetic relationship matrix, which is similar to the concept of a distance matrix in geospatial modeling, though in this case the distance is genetic similarity calculated from the genome-wide SNP data. Therefore, genetic effects are associated with the covariance matrix for common SNPs (called A) and non-genetic effects with the identity matrix (called I). Using the identity matrix for this purpose assumes no shared environment effects, which is valid since only unrelated persons are included in the calculation. We routinely assess age, sex, and socioeconomic status as covariates, and always include ancestry principal components. SNP-based heritability can be performed on case-control datasets, population cohorts or other collections of unrelated individuals. Thus, while traditional heritability assumes zero genetic covariance between “unrelated” persons, observed SNP-based genetic covariance will rarely if ever be zero. The cohort includes mostly unrelated individuals (55 sets of twins/triplets). Rather than model the relationships among related individuals and lose power from increased degrees of freedom, we will apply a resampling procedure. Sampled datasets with 1 twin chosen at random ensures the datasets in each replicate contain only unrelated persons but the average over the sampled datasets converges on estimates that use information from all children. In our cohort we will have $>80\%$ power to detect SNP-based heritabilities as low as 21%, after accounting for the resampling procedure. While fatty acid markers have not explicitly been tested this way before, the relationship between genetics and many metabolism biomarkers in blood is much higher than a heritability of 21%, giving further reassurance that the study is adequately powered. The test of *en masse* SNP effects in the context of this clinical trial takes the form similar to Aim 1, $y_{it} = \beta_0 + \beta_1 Time_{it} + \beta_2 Trt_{it} + \beta_3 g + \beta_4 Trtxg + \beta_5 Timexg + \beta_6 Time_i Trt_i + \beta_7 Time_i x Trtxg_i + \epsilon_{it}$, while the constraints on V are still imposed. The matrix A will be estimated using the software GCTA and the model will be tested using R or Python depending on whether numerical issues arise in the numerical matrix calculations. We can perform this model using structural equation models implemented in the R library genomicSEM. This modeling platform will allow us to use *en masse* SNPs in the models described above.

To address the second part of Aim 2, our primary tests will be conducted using 2 linear mixed models similar to that described above in Aim 1. We will estimate the effect of treatment assignment on our 3 primary outcomes at age 8 ½ - 10 ½ (DAS-II GCA, CELF-5 language, Toolbox EF) except that the interaction of treatment by time will include one SNP at a time. These two genetic variants come from the two previously identified SNPs in the literature that we selected as the primary SNPs of interest for this study (SNPs rs1535, rs174575 in the *FADS2* gene). We will be conducting a test of null hypothesis that each SNP has no interaction affecting the outcome. Using the model terminology from Aim 1, $y_{it} = \beta_0 + \beta_1 Time_{it} + \beta_2 Trt_{it} + \beta_3 SNP_i + \beta_4 TrtxSNP_i + \beta_5 TimexSNP_i + \beta_6 Time_i Trt_i + \beta_7 Time_i x TrtxSNP_i + \epsilon_{it}$, where SNP_i is defined as two groups based on the presence/absence of the rare allele at that locus. Last, although we will make efforts to have DNA from every child, some parents may refuse or sample quality could

PROTOCOL TITLE: Long-term Effects and Safety of DHA+AA Supplementation in Toddlerhood for Children born Preterm

occasionally be compromised. We will treat missing genetic data just as for other missing data (see Aim 1 – Statistical Analysis).

Analysis plan for secondary outcomes:

Secondary outcomes will be analyzed as for the plan listed above for Aim 1, with the exception that binary outcomes will use logistic or log-binomial models. Secondary outcomes have been specified under section 4.0 Study Endpoints. Results will not be adjusted for multiple comparisons because of the pitfalls of that approach (see Rothman, Epidemiology 1990).

Exploratory analysis of genetic data:

The genetic data in this study, when combined with publicly available SNP by gene transcription reference datasets allows investigators to impute gene transcription values using bioinformatics software such as PrediXcan, FUSION, or TIGAR. All methods use the estimated change in gene transcript per SNP allele to provide an overall estimate of the relative gene expression of the given gene when provided genomewide SNP data. The main advantage of analyzing surrogate gene expression values in this context is that we may interrogate specific genes of physiological or metabolic interest one by one with the clinical outcomes. This procedure generates mechanistic hypotheses for testing in future studies on both humans and model organism. The analysis is necessarily exploratory due to sample size limitations. To prevent excessive loss of power due to transcriptome-wide testing (i.e., testing all genes) we will limit our analysis to genes related to cellular fatty acid processing. The same model form from Aim 1 would be ideal, though in this case some variable selection is likely to be needed. We prefer LASSO regression to select genes with main effects, and test only those genes in the mixed model from Aim 1.

Repeated measures:

When the same or similar outcome measure has been made repeatedly during the original trial plus follow-up study (e.g., weight, global cognitive composite), the analyses described above under Aim 1 will be augmented to accommodate additional timepoints.

Additional analyses:

Fatty acid levels at trial baseline, the end of the trial, the change in values between those timepoints, and calculated dietary intakes of long-chain fatty acids at ages 8 ½ - 10 ½ will be correlated with the outcome measures. This analysis will not be per intent to treat.

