2.1 Hypotheses & Aims

Our central hypothesis is that preterm children who were randomized to 180 days of DHA+AA at age 1 will exhibit poorer general cognitive ability, greater language deficits, and more impaired executive function at age 8½ -10½ vs children randomized to placebo. Our hypothesis has been formulated primarily on the findings from Omega Tots and DINO, the largest DHA-supplementation trial of preterm infants. The rationale for this project is that a careful examination of the long-term effects of DHA+AA supplementation will offer much-needed clarification about the appropriateness of DHA+AA as an intervention to promote neurodevelopment among children born preterm. We plan to pursue our central hypothesis and accomplish our objective by pursuing the following specific aims:

Aim 1: Determine the long-term effect of DHA+AA supplementation at age 1 year by comparing general cognitive ability, language, and multiple facets of executive function between the DHA+AA and placebo arms at age 8-9.

- Based on our preliminary data, working hypothesis 1 is that children randomized to DHA+AA at age 1 will display at least a 0.3-SD (effect size) deficit on measures of general cognitive ability, language, executive function at age 8½ - 10½ vs placebo.
- Sub-aim 1: Explore sub-group differences by sex, birthweight, socioeconomic status, and diet.

PROTOCOL TITLE: Long-term Effects and Safety of DHA+AA Supplementation in Toddlerhood for Children born Preterm

Aim 2: Determine the role of variability in fatty acid metabolism genetics en masse on the effect of DHA+AA supplementation on short and long-term outcomes, and further focus on 2 previously published FADS2 genetic variants.

- Based on prior observational studies, working hypothesis 2a is that common genetic variant-based heritability over long-chain fatty acid metabolism will be associated with poorer performance on our outcome assessments at ages 1, 2, and 8½ - 10½ years for children assigned to DHA+AA vs placebo. Genetic variation is based on measured SNPs in genes accounting for virtually all synthesis of very long-chain fatty acids. Further, we hypothesize (2b) that minor allele status for FADS2 rs1535 and rs174575, the most commonly replicated SNPs in the literature, will be associated with poorer outcomes for children assigned to DHA+AA, vs placebo.

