Omega-3 docosahexaenoic acid (DHA) dietary supplements have been touted to promote cognitive development in preterm children based on large RCTs showing short-term visual and cognitive benefits in infancy. DHA is added to virtually all infant formula products as a result. DHA is the dominant structural omega-3 fatty acid in the brain, where it rapidly increases in concentration to age 2 and is a key player in numerous neurologic processes. Some families continue supplementation beyond infancy in the hope of further benefit, despite no evidence for efficacy post-infancy. Our recent Omega Tots trial filled that gap by testing the effect of 180 days' supplementation with DHA plus omega-6 arachidonic acid (AA) vs placebo in 377 preterm toddlers. Interestingly, we observed adverse effects of DHA+AA supplementation on early effortful control and language development in 2 pre-specified sub-groups, and no developmental benefit. Six months' post-trial, we saw adverse effects for the entire DHA+AA group: a 0.3-SD deficit in global cognitive development scores. The Australian DINO trial supplemented preterm infants and reported negative effects on executive function 4-7 years later. However, all these adverse findings were based only on parent report. Biologic explanations for adverse effects remain entirely unexplored, but fatty acid desaturase genetic polymorphisms (SNPs) are top candidates because of their strong effects on the amount and balance of long-chain fatty acids available to the developing brain. Therefore, there is an urgent need to evaluate trial participants in more depth, long term, to ensure that DHA+AA supplementation is not causing lasting harm. Without such information, the estimated 3.3 million US children annually who consume supplemented formula and foods will continue to be exposed

PROTOCOL TITLE: Long-term Effects and Safety of DHA+AA Supplementation in Toddlerhood for Children born Preterm

without reassurance. This is particularly worrisome for children born preterm who are already at risk for cognitive deficits.

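### The Aim 1 power statement is set at 0.32 SD, but Hypothesis 1 starts at 0.3 SD, where 300 children give about 74% power, before any allowance for siblings

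*Combined protocol and SAP*

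**What the plan says.** The Aim 1 power paragraph in section 17.1 assumes that 300 of the 377 randomised children attend. It states that "300 children divided equally to each arm provides >80% power to detect a 0.32-SD mean difference or larger" for each of the three primary measures at an alpha of 0.05, and it labels this as power for Hypothesis 1. It gives no sidedness, no allowance for siblings and no gain from baseline adjustment.

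The paragraph justifies 0.32 SD by earlier results: "This effect size is the same or smaller than what the DINO trial observed on the BRIEF at age 7". The same sentence extends the comparison to two Omega Tots results, the ECBQ and the DP-3 at age 2, without giving a size for any of the three.

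Two other sections give the figures to compare:

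- Section 2.1, working hypothesis 1: children given DHA+AA "will display at least a 0.3-SD (effect size) deficit" on the primary domains.
- Section 3.0: six months after the trial the supplemented group showed "a 0.3-SD deficit in global cognitive development scores".

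On siblings, the Aim 1 analysis text adds a family-level random effect for twins and triplets. The Aim 2 text counts 55 such sets in the cohort.

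**The concern.** A power statement attached to a hypothesis should cover the smallest effect that the hypothesis names. Here the hypothesis begins at 0.30 SD and the power is quoted at 0.32 SD. The Aim 1 analysis text goes on to say that lasting effects of the anticipated size could be detected, so the reader is led to carry the 80% figure back to the anticipated effect.

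The stake is the reading of a null result. Section 2.1 expects the study either to reassure about the safety of supplemented products or to draw attention to harm. How far a null result reassures depends on how likely the study was to miss harm of the size it set out to find.

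**Working it through.** **Inputs.** 150 per arm, alpha 0.05 and 0.32 SD come from section 17.1. The 0.30 SD comes from sections 2.1 and 3.0, and the 55 sibling sets from the Aim 2 text of section 17.1. The two-sided test, the sibling intraclass correlation (ICC), the sibling allocation and the baseline–outcome correlation are not given, so they are assumptions below.

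**1. The plan's own figure.** For a two-sample comparison on the SD scale, the noncentrality is d × √(n/2), with n per arm.

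- d = 0.32: 0.32 × √75 = 2.77. Normal approximation: Φ(2.77 − 1.96) = 79.1%. Noncentral t: 78.9%.
- Effect detectable with 80% power: (1.960 + 0.842) × √(2/150) = 0.3235 SD (normal), or 0.3245 SD (noncentral t).

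The figure reproduces within rounding, although strictly it is just under 80%. A one-sided test would give 87% at 0.32 SD, so two-sided is the reading that fits the plan's number.

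**2. The hypothesised floor.**

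- d = 0.30: 0.30 × √75 = 2.60. Normal: 73.8%. Noncentral t: 73.6%.
- Chance of missing it, per outcome: 1 − 0.736 = 26%.
- 80% power at 0.30 SD needs 176 per arm by noncentral t. That is 352 children, and 352/377 = 93% attendance.

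**3. The comparison with earlier results.** Enrolment was at 10–16 months corrected age. Adding about 6 months of treatment and 6 months after it gives about 22–28 months, so the 0.3 SD result in section 3.0 appears to be the DP-3 result at age 2. As printed, 0.32 is larger than 0.3. A value printed as 0.3 could lie anywhere from about 0.25 to 0.35, where power runs from 58% to 86%.

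**4. Siblings.** Treat all sets as twin pairs, in proportion to attendance (55 × 300/377 ≈ 44 pairs among the 300).

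If siblings share an arm, the design effect is 1 + (88/300) × ICC:

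| Assumed ICC | Design effect | Effective N | Power at 0.30 | Power at 0.32 |
|---|---|---|---|---|
| 0.3 | 1.09 | 276 | 70% | 75% |
| 0.5 | 1.15 | 262 | 68% | 73% |
| 0.7 | 1.21 | 249 | 65% | 71% |

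This uses simple arm means. The planned mixed model weights pairs more efficiently and gives about 68–71% at 0.30 SD over the same ICC range.

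If every pair is split between arms, the information is 212/4 from singletons plus 44/[2(1 − ICC)] from pairs. Power at 0.30 SD is then about 79% at ICC 0.3 and 92% at ICC 0.7.

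**5. Baseline adjustment.** With correlation r, the residual SD is √(1 − r²). Power at 0.30 SD is 75.5% for r = 0.2 and 77.7% for r = 0.3, and about r = 0.38 is needed for 80% (normal approximation).

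**The case against.** The strongest reply is that nothing here is miscalculated. The detectable effect of 0.3245 SD rounds to the plan's 0.32, and a hypothesis of at least 0.3 SD includes 0.32. That stands: this is not an arithmetic error. What remains is that the quoted power does not reach the floor of the hypothesis it is attached to.

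A reader might infer that the plan calls 0.32 SD no larger than the effect it expects. It does not. The comparison is with effects observed in DINO and Omega Tots. The DINO and ECBQ sizes are not in the documents, so those comparisons cannot be challenged. The age-2 comparison can be questioned only as printed; an unrounded value of 0.32 or more would settle it in the plan's favour.

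A reader might also infer that sibling clustering is ignored, or that it must cost power. Neither follows. The analysis models it, only the power statement omits it, and its effect can go either way because neither the allocation of siblings nor an ICC is given.

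Other points narrow the gap. The plan calls 300 conservative, and all 377 would give 83% at 0.30 SD. A one-sided test would also give 83%. Baseline adjustment may help, but the plan claims no such gain, and section 17.1 concedes that comparable developmental measures do not exist at all time points. Finally, the 26% is per outcome, and harm present on all three outcomes is no more likely to be missed on every one of them.

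**Conclusion.** The point holds as a mismatch between the power statement and the plan's own hypothesis. At the 0.30 SD floor, 300 children give about 74% power per outcome, and 80% is reached at about 0.325 SD. This assumes a two-sided 0.05 test, equal arms, independent children and no baseline gain. Sibling allocation could move the 74% down to about 65–70% or leave it unchanged or higher.

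The documents do not support calling the cohort inadequate or the analysis unsound. The sample is fixed and the shortfall is moderate. The correction matters mainly for how firmly a null result may be read as reassurance.

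**What to change.** Keep the sample and amend the Aim 1 power paragraph in section 17.1:

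1. Restate the power, for example: *With 300 children (150 per arm) and a two-sided 0.05 test, power is about 74% at the hypothesised 0.30 SD; 80% power is reached at about 0.325 SD, before any allowance for siblings or baseline adjustment.*
2. Add the figure adjusted for the sibling allocation, which is known from the original trial, and state the ICC assumed. If a baseline gain is to be claimed, state the correlation assumed.
3. Give the unrounded age-2 effect in support of the comparison, or remove that part of the sentence.
4. State that any reassurance from a null result will rest on the corrected detectable effect and on the confidence interval for the treatment difference.

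The cost is a wording amendment. The downside is a slightly less favourable stated figure.
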